3. STUDY PLAN AND PROCEDURES

3.1 Overall study design and flow chart

This is a 26-week, single-center, randomized, single-blinded to the investigators, open-label, 2-period crossover phase IV clinical trial comparing 12-weeks of glycemic intervention with dapagliflozin versus glimepiride on measures of HRV. The two periods will be separated by a 2-week wash-out period. All subjects will be allocated and randomized to each treatment sequence in a 1:1 fashion. Participants will receive either dapagliflozin 5 mg or glimepiride 2 mg daily initially for 4 weeks then titrating the dose gradually up to dapagliflozin 10 mg daily or glimepiride 4 mg daily (no more than 4 mg daily) as needed based on glucose monitoring for 8 more weeks (total 12 weeks) followed by 2-week washout period. Then they will receive the study drugs in reverse order to the first period for another 12 weeks. Glucose variability will be also assessed using Abbott's Freestyle Libre Pro CGM for 2-week during each intervention period.

Figure 1: Proposed study design

[figure not shown]

Table 1: Proposed visit schedule

	Period 1					Wash-out	Period 2			
Visit Numbers	Visit 1	Visit 2	Visit 3	Visit 4	Visit 5		Visit 6	Visit 7	Visit 8	Visit 9
Visit Description	Screening	Baseline Visit (Study Drug 1)	Monitoring	Monitoring	End of Study Drug 1	N/A	Baseline Visit (Study Drug 2)	Monitoring	Monitoring	End of Study Drug 2
Time point	Day -30 to 0	Day 0	Week 4	Week 8	Week 12	Week 13-14	Week 15	Week 19	Week 23	Week 26
Visit window	1 month	± 7 days	± 7 days	± 7 days	± 7 days	NA	± 7 days	± 7 days	± 7 days	± 7 days
Informed consent and HIPPA ¹	X									
Medical history	X				X		X			X
Physical exam ²	X				X					X
Inclusion/Exclusion criteria	X									
Concomitant medications	X						X			
Vital signs	X	X	X	X	X		X	X	X	X
Urine analysis, urine β-HCG test in women of childbearing age	X									
Venous blood A1C	X				X					X
CBCP, FBG, comprehensive metabolic profile, , lipid profile, and urine albumin excretion	X				X					X
TSH	X									
BNP	X				X		X			X

ECG	X				X		X			X
HRV		X			X		X			X
CARTs		X			X		X			X
CGM				2 weeks					2 weeks	
Assess hypoglycemia		X	X	X	X		X	X	X	X
Record Adverse Events (AEs), Serious Adverse Events (SAEs)		X	X	X	X			X	X	X
Assessment of compliance by counting pills			X	X	X			X	X	X

¹ The informed consent form must be signed before any study procedure is performed.

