5.2.3 Assessments

CAN

A. Heart rate variability (HRV) studies: low and high frequency power (LF,HF), and time domain measures of HRV, standard deviation of normal RR interval(SDNN), root mean square of successive RR intervals (RMSSD) are analyzed from continuous ECG recordings using the ANX 3.1 software (ANSAR Inc., Philadelphia , PA) as described [35, 36].

B. Cardiovascular reflex tests will include: 1) changes in R-R interval with deep breathing, a measure of sinus arrhythmia during quiet respiration reflecting primarily parasympathetic function; 2) the R-R response to standing, inducing reflex tachycardia followed by

bradycardia which is jointly vagal and baroreflex-mediated; 3) the Valsalva ratio which evaluates cardiovagal function in response to a standardized increase in intrathoracic pressure (Valsalva Maneuver); and 4) orthostatic changes in BP. These tests are reproducible and considered as gold-standard [36, 37].

C. Resting heart rate

Subjects will be asked to avoid food, caffeine and tobacco products for at least 8 hours prior to testing, and hold any medication until testing was completed. Subjects who experienced a hypoglycemic episode after midnight [blood glucose \leq 50mg/dl (2.77mmol/l)] prior to the testing were rescheduled.

Cardiac function

We will measure serum BNP, by Chemiluminescent Immunoassay (CLIA) (Siemens, Erlangen, Germany) and will evaluate changes in BNP, as a biomarker for LV function. The blood draw will be performed at baseline and end of each study drug period.

Assessment of glucose variability

We will use a 14-day continuous glucose monitoring (CGM) using Abbott's Freestyle Libre Pro to evaluate and compare the indices of glucose variability [mean glucose, standard deviation (SD), coefficient of variation (CV), the mean amplitude of glycemic excursions (MAGE), low blood glucose index (LBGI) and area under the curve (AUC) for hypoglycemia] during each dapagliflozin and glimepiride intervention phase in patients with type 2 diabetes and also assess the association between the indices of glucose variability and changes in measures of HRV during each intervention period.

5.3 Procedures for handling subjects incorrectly enrolled or randomized or initiated on investigational product

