6.2 Data collection at enrollment and follow-up

The following data will be collected at enrollment periods (for each study drug period):

1. Vital signs: BP, weight, BMI, HR
2. Blood sample for safety laboratory assessments, glucose control and biomarker for cardiac function (CBCP, CMP including FBG, HbA1c, lipid panel and urine albumin assessment, BNP) (See Table 1)
3. ECGs for heart rate variability studies (LF, HF, LF/HF ratio, SDNN and RMSSD), cardiovascular autonomic reflex tests (E/I ration, Valsalva ratio, 30:15 and orthostatic BP) and RHR
4. Assessment of hypoglycemia by evaluating symptoms and downloading glucometers and glucose log sheets

During follow-up monitoring visits, we will assess hypoglycemia (symptoms, recordings) vital signs, any changes in their medication list, recording of adverse events, serious adverse events and compliance and tolerability of study medications.

At the end of each intervention period, we will repeat the same measures and procedures to obtain primary and secondary endpoints. Those include blood sample for biomarkers, HRV, and CARTs.

We will also evaluate the indices of glucose variability by using Freestyle Libre Pro CGM during each intervention phase in this cohort.

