12.2 Methods of statistical analyses

The primary objective of this trial is to compare the change in the LF: HF ratio from baseline to 12 weeks for patients on dapagliflozin versus glimepiride.

The mean change in LF: HF ratio for each drug from baseline to 12 weeks will be reported with the corresponding 95% confidence interval. The mean difference between drugs of changes from baseline to 12 weeks and the corresponding 95% confidence interval will also be reported. The change from baseline to 12 weeks within each period (between drugs) will be compared within patients using a two-sided t-test (applying transformations where appropriate; using the pharmacodynamics set of subjects). This analysis will be repeated using the ITT set of subjects. If there is chance within-subject or between-subject imbalance in baseline measures (such as glucose control, BMI and age), we will use the ANCOVA method including those unbalanced covariates to improve precision (Metcalf, *Statistics in Medicine, The analysis of cross-over trials with baseline measurements*, 2010).

A corresponding primary analysis to the t-test controlling for possible sequence and period effects includes a linear mixed effects model (also known as random effects model; applying transformations where appropriate) with outcome of the change in LF: HF ratio from baseline to 12 weeks. This model assesses the difference between drugs by accounting for a

random effect for subject (nested within sequence) and fixed effects for treatment, sequence, and period.

We will additionally explore differences between the drugs over time using all of the data measured at baseline, 4, 8 and 12 weeks with a linear mixed model. The outcome will be the change from baseline at 4, 8 and 12 weeks. The model will include a random term for subject nested within sequence and fixed effects for treatment, sequence, visit, period, and interaction terms for visit by treatment. The interaction terms for visit by treatment provide estimates of treatment effects at each visit. An unstructured variance/covariance matrix will be used.

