All secondary endpoints will be similarly compared where each endpoint for each drug will be measured at baseline and 12 weeks and the difference within each drug will be compared within patients using a two-sided t-test (applying transformations where appropriate). Similar to the analysis for the main outcome, linear mixed effect models with an unstructured variance/covariance matrix and outcomes of changes from baseline at 4, 8, and 12 weeks will assess changes over time for each outcome. The mixed effects models will include a random effect for patients nested within sequence and fixed effects for treatment, sequence, visit, period and the interaction between treatment and visit.

Associations between the indices of glucose variability and changes in measures of HRV during each intervention will be analyzed using paired t-tests or Wilcoxon signed rank test (if normality assumption is violated). Effect sizes will be estimated with 95% confidence intervals of the associations between glucose variability and changes in measures of HRV within each intervention using linear regression (applying transformations when necessary). If period effects are found from our primary analysis, we will control for the period in which the drug was given within the model. The interaction between drug and glucose variability on the changes in measures of HRV will be explored using a generalized estimating equations (using an unstructured working correlation matrix since we only have 2 observations per person). We will not control for multiple comparisons and expect results to be validated in a future independent cohort.

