12.3 Determination of sample size

We assume there are no carryover effect and no interactions between patients, treatments, and time period. For each patient in each period (on each drug), the LF: HF ratio will be measured at baseline and at 12 weeks. The primary outcome will be the difference between periods (drugs) in the differences from baseline to 12 weeks of the LF: HF ratio (i.e. [LF: HF sulfonylurea, week12 – LF: HF sulfonylurea, baseline] – [LF: HF dapagliflozin,

week12 – LF: HF dapagliflozin, baseline]). Based on previous studies, we have found the LF: HF ratio to have a mean of 3.4 (SD=2.1) for those with T2D. Assuming a similar within person standard deviation (2.1) of the difference of the differences in the LF: HF ratio from baseline to 12 weeks, we have 80% power with 38 patients to find a difference between the two drugs in the differences in LF: HF ratios of 1.4 using a two-sided (paired) t-test at the 0.05 significance level (sample size from applet available at http://hedwig.mgh.harvard.edu/sample_size/js/js_crossover_quant.html). Expecting 10% of the subjects to not complete the entire study, we plan to enroll 45 patients.

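### Section 12.2 promises week-4 and week-8 treatment effects for endpoints that are measured only at baseline and week 12, and names paired tests for an association question

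*Combined protocol and SAP*

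**What the plan says.** **Longitudinal models.** After the primary t-test and a mixed model with treatment, sequence and period effects, Section 12.2 adds an exploratory analysis of LF:HF "using all of the data measured at baseline, 4, 8 and 12 weeks with a linear mixed model". The outcome is change from baseline at the three post-baseline times, with an unstructured covariance matrix. Of the model's output it says: "The interaction terms for visit by treatment provide estimates of treatment effects at each visit". For the secondary endpoints it plans the same kind of model, whose "outcomes of changes from baseline at 4, 8, and 12 weeks will assess changes over time for each outcome".

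**Measurement times.** The same section says of the secondary endpoints that "each endpoint for each drug will be measured at baseline and 12 weeks". Section 12.3 says that in each period "the LF: HF ratio will be measured at baseline and at 12 weeks". In Section 3.1, "Table 1: Proposed visit schedule" marks HRV and CARTs at Visits 2, 5, 6 and 9 only, and BNP at Visits 1, 5, 6 and 9 only. Section 5.2.3 says of BNP: "The blood draw will be performed at baseline and end of each study drug period". Section 6.2 says: "At the end of each intervention period, we will repeat the same measures and procedures to obtain primary and secondary endpoints".

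**CGM indices.** Sections 2.4 and 5.2.3 set two aims: to compare the glucose-variability indices between drugs, and to assess their association with HRV change. For the association, Section 12.2 names a paired t-test, with the signed-rank test as the non-normal alternative. It then names linear regression for effect sizes and GEE for the drug-by-index interaction. It names no test for the between-drug comparison.

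**The concern.** A visit-specific treatment effect needs outcome data at that visit. If nobody has an HRV, CART or BNP value at week 4 or 8, this is not missing data that a mixed model can absorb. The values are absent by design for every participant, and the analyst would have to depart from the written model for every primary and secondary endpoint in Section 6.

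The second problem is a mismatch of test and question. A paired test asks whether two measurements have the same centre. Applied to a glucose index and an HRV change, it returns a p-value unrelated to whether the two move together. Followed literally, the plan would report such p-values as evidence about association, and the between-drug CGM comparison would be left to a choice made after the data are in.

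**Working it through.** **1. Which endpoints have week-4 and week-8 data.** Weeks 4 and 8 of each period are Visits 3 and 4, and Visits 7 and 8.

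| Outcome | Visits in Table 1 | Week 4 or 8 value? |
|---|---|---|
| LF:HF, SDNN, rmsSD (HRV) | 2, 5, 6, 9 | No |
| E/I, Valsalva ratio, 30:15 (CARTs) | 2, 5, 6, 9 | No |
| BNP | 1, 5, 6, 9 | No |
| Resting heart rate, BP, weight (vital signs) | all nine | Yes |

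This is not an artefact of a broken table. The Section 5.2.2 narratives for Visits 3, 4, 7 and 8 list vital signs, glucometer download, compliance and adverse events, with CGM placement at Visits 4 and 8. The case report form overviews for those visits have no HRV, CARTs or laboratory line. Section 12.2 itself, when it specifies the GEE, counts two observations per person.

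**2. Data available to the model.** Section 12.3 needs 38 completers and enrolls 45. (The 38 reproduces, with power 0.808, if 2.1 is the within-patient SD, so that the paired difference has SD 2.1 × √2 = 2.97. Here it serves only to count rows.) The model expects 3 visits × 2 periods = 6 change values per person; the schedule supplies 1 × 2 = 2.

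- 38 completers: 38 × 2 = 76 of 38 × 6 = 228.
- 45 participants: 45 × 2 = 90 of 45 × 6 = 270.

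**3. Estimability.** The fixed-effect columns are intercept, treatment, sequence, period, visit 8, visit 12, visit 8 × treatment and visit 12 × treatment: 8 in all.

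- Rows at weeks 4, 8 and 12: rank 8, and all three visit-specific treatment effects are estimable.
- Rows at week 12 only: the visit-8 and visit-8 × treatment columns are all zero, the visit-12 column equals the intercept, and the visit-12 × treatment column equals treatment. That leaves intercept, treatment, sequence and period, so the rank is 4.

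A contrast is estimable if appending it to the design does not raise the rank. With week-12 rows only:

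- treatment at week 4: not estimable;
- treatment at week 8: not estimable;
- the two visit and two visit-by-treatment coefficients: none separately estimable;
- treatment at week 12, sequence and period: estimable.

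The surviving design spans the same space as the treatment, sequence and period model that Section 12.2 already gives alongside the primary t-test.

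**4. Covariance.** Two values per person support at most 2 × 3 / 2 = 3 covariance parameters. An unstructured matrix needs 3 × 4 / 2 = 6 for three visits, or 6 × 7 / 2 = 21 for three visits in each of two periods.

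**5. Paired test against slope test.** The argument is logical; the simulation only illustrates it (20,000 trials, n = 38, two-sided 0.05, all inputs assumed).

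- *No association.* Mean glucose 80, 130 or 180 mg/dl (spanning the home targets in Section 5.2.2), between-person SD 15, 30 or 60 mg/dl. LF:HF change is independent of glucose, with mean 0 and SD 2.1 (the SD figure in Section 12.3). In all nine combinations the paired t-test rejects in 100% of trials and the slope test in 4.9% to 5.3%.
- *Equal location, real association* (both variables mean 0, SD 1). At correlation 0.3 the paired test rejects in 4.8% and the slope test in 45.8%. At correlation 0.6 the figures are 4.9% and 98.5%.

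**The case against.** The strongest reply concerns weight. The LF:HF longitudinal model is expressly exploratory, the week-12 analyses are stated before it, and the model collapses to one already in the plan. Dropping a factor with a single observed level changes no estimate, error rate or sample size. All of that stands, and it limits the consequence. It does not make the promised week-4 and week-8 effects available.

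Nor is the model wholly without data. Resting heart rate is part of the primary objective and of the CAN assessments in Section 5.2.3; BP and weight are secondary objectives; all three are taken at weeks 4 and 8. Section 6.2 also lists them among the measures collected at the start of each period, before saying that the same measures are repeated to obtain the endpoints. So a longitudinal model could be fitted to them. But the endpoint list that opens Section 6 omits them, and Section 12.2 names LF:HF as the outcome and models the secondary endpoints in the same way.

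On the CGM sentence, the likely explanation is that two aims were merged: the paired test suits the between-drug comparison, and the regression and GEE suit the association. That is plausible, and it means valid association methods are already prespecified. The text still assigns the paired test to the association and no test to the comparison. It is also fair to say that the 100% rejection rate follows from pairing quantities on different scales; it illustrates the mismatch and does not forecast a result.

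**Conclusion.** Both points hold. For all seven Section 6 primary and secondary endpoints, 2 of the 3 visit-specific treatment effects that Section 12.2 promises cannot be estimated, because 4 of the 6 expected change values per person are never collected. This rests only on the visit schedule, which the visit narratives, Sections 6.2 and 12.3 and the case report forms confirm. The week-12 treatment contrast is unaffected, so neither the primary conclusion nor the secondary week-12 conclusions are at risk.

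The paired test named for the CGM association does not test association. That follows from what the test compares and does not depend on the simulation inputs. The effect is confined to exploratory endpoints, but the p-values would mislead if the sentence were followed as written, and the between-drug CGM comparison has no prespecified test. Both points should be corrected before analysis.

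**What to change.** - **Section 12.2, HRV, CARTs and BNP:** delete the week-4/8/12 models and the statement about effects at each visit. State the week-12 mixed model with treatment, sequence and period effects for each endpoint.
- **If a longitudinal model is kept:** limit it to resting heart rate, BP and weight, name them in Section 12.2, and add them to the Section 6 endpoint list.
- **Section 12.2, CGM indices:** test association with HRV change only by the linear regression and GEE already named. Assign the paired test, or a period-adjusted version, to the between-drug comparison of the indices.

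The cost is wording in Section 12.2, and in Section 6 if the three vital-sign outcomes are added. No new visits, samples or data are needed.

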We also plan to evaluate the indices of glucose variability and its association with changes in CAN parameters in patients with type 2 diabetes during each dapagliflozin and glimepiride treatment period. Glucose variability is also associated with an increased risk of hypoglycemia, which is an important barrier in sustaining intensive treatment in patients with diabetes [28, 29]. Recurrent severe hypoglycemia, besides inducing alterations in cardiac electrical stability and QT interval prolongation, may contribute to alter the cardiac autonomic function and the cardiovagal balance, increasing the risk of cardiac arrhythmia in patients with diabetes [30, 31]. Theoretically, given the higher propensity for hypoglycemia, sulfonylurea may induce more glycemic variability than SGLT-2 inhibitors. Currently no studies evaluated directly the changes in daily glucose excursions with these commonly prescribed agents were done. Thus, adding a component continuous glucose monitoring with the Abbott's Freestyle Libre Pro for 2 weeks during each sulfonylurea and SGLT-2 inhibitor intervention phase in this T2D cohort, will enable performing additional analyses linking effects of medications on daily glucose profiles with measures of heart rate variability and heart function, that could unveil important data on CVD risk with a minimal additional cost.

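### No planned glucose-variability analysis isolates the within-patient link between drug differences in CGM indices and drug differences in HRV change

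*Combined protocol and SAP*

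**What the plan says.** Section 12.2 gives three tools for this question.

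- Paired t-tests, or Wilcoxon signed rank tests if normality fails, are said to analyse the associations.
- Effect sizes with 95% confidence intervals are to come from "associations between glucose variability and changes in measures of HRV within each intervention using linear regression". Period is added only if the primary analysis shows a period effect. No other covariates are named.
- A GEE with unstructured working correlation is to explore the drug-by-index interaction.

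The section plans no multiplicity control and expects validation in a later cohort.

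The aim is described in two ways. Section 5.2.3 plans to "assess the association between the indices of glucose variability and changes in measures of HRV during each intervention period", and sections 2.4 and 6 have the same per-phase aim. Section 1.3 justifies the CGM component because it "will enable performing additional analyses linking effects of medications on daily glucose profiles with measures of heart rate variability and heart function".

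Section 5.2.2 and Table 1 schedule one two-week CGM recording in each treatment period, after Visits 4 and 8. HRV is measured at the start and end of each period. No off-drug CGM recording is scheduled.

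**The concern.** The purpose in section 1.3 is a within-patient question: when a patient's glucose variability differs between the two drugs, does the HRV change differ too? A regression run separately for each drug compares patients with one another. Any stable characteristic related to both the index and the HRV response can then produce a slope, and a real within-patient link can be diluted. The conditional period term does not help, because within one drug period and sequence are the same variable.

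The primary comparison in 12.2 is made within patients; the per-drug regressions are not. At stake is the meaning of the slopes that would be carried forward to the validation cohort.

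**Working it through.** **Inputs from the documents.** The plan gives no power or effect size for this association, so there is no figure of its own to reproduce. I took n=38 from section 12.3 ("we have 80% power with 38 patients"). That figure reproduces when 2.1 is the within-patient SD per period: the SD of the difference is 2.1 × √2 = 2.97, and a t-based calculation for a difference of 1.4 at two-sided 0.05 gives N=38 with 80.8% power. (With 2.1 as the SD of the difference of differences, as section 12.3 words it, N would be 20. That is a separate matter and does not bear on this point.) For enrolment, 45 × 0.9 = 40.5, so some simulations use n=40.

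**What a per-drug slope estimates.** Scale the index to unit variance and let its intraclass correlation (ICC) across the two periods be ICCx. Let B be the slope of HRV change on the patient's stable index level, and W the slope on that patient's deviation from it. Then

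per-drug slope = ICCx × B + (1 − ICCx) × W,

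whereas regressing the between-drug difference in HRV change on the between-drug difference in the index estimates W alone.

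**False association (W = 0).** Assume that HRV change, also with unit variance, has intraclass correlation ICCy and that the two patient components correlate at c. The induced correlation is c × √(ICCx × ICCy); for example 0.4 × √(0.6 × 0.2) = 0.14. Results from 6,000 simulations per setting, n=38, nominal 5%:

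| ICCx, ICCy, c (assumed) | Induced r | Per-drug rejection | Within-patient rejection, with sequence term |
|---|---|---|---|
| 0.6, 0.2, 0.4 | 0.14 | 12.4% | 5.1% |
| 0.5, 0.3, 0.5 | 0.19 | 21.9% | 4.9% |
| 0.6, 0.3, 0.5 | 0.21 | 26.0% | 4.6% |
| 0.6, 0.4, 0.7 | 0.34 | 58.6% | 4.8% |
| 0.6, 0, 0.5 | 0 | 4.2% | 5.2% |

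A wider grid used n=40, 1,500 runs per setting, ICCx 0.5 to 0.8, ICCy 0.2 to 0.5 and c 0.3 to 0.6. It gave 9% to 69% for one per-drug regression, 17% to 86% for at least one of the two, and 4% to 6% for the difference regression.

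**Missed association (W = 0.5, B = 0).** The formula gives 0.5 × (1 − 0.5) = 0.25 at ICCx 0.5 and 0.5 × (1 − 0.8) = 0.10 at ICCx 0.8. With ICCy = 0 and n=40, the simulated mean slopes were 0.25 and 0.10 (power 31% and 9%), against 0.49 and 0.51 for the difference regression (power 56% and 29%). This dilution needs no confounder, but it does assume B = 0. If B equalled W there would be none.

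**The GEE.** In the five tabulated settings (n=38, 4,000 runs, robust standard errors), the drug-by-index interaction rejected in 6.1%, 6.4%, 6.1%, 6.8% and 6.4%. The last setting has no induced correlation, so the excess over 5% is consistent with small-sample error in the robust standard error. A further simulation put the rate at 5% to 9% whether or not the factor was present. An index main effect is different: in a GEE with index and drug but no interaction, it rejected in 11% to 78% over the wider grid.

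**The case against.** Four objections deserve an answer.

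1. *The stated objective is association within each phase.* Sections 2.4, 5.2.3 and 6 say so, and the per-drug regressions answer it. This stands. The gap is only against the purpose in section 1.3, so the regressions should stay.
2. *The outcome is already change from each period's own baseline*, so stable differences in HRV level are gone. Inflation needs a stable tendency for HRV to change similarly on two different drugs, linked to the index. This stands. The documents give no such figure. Section 12.3 assumes no interaction among patients, treatments and periods; with independent errors that makes ICCy zero. With serially correlated HRV (assumed exponential decay, 12-week correlation 0.1 to 0.7), the two changes would correlate at about −0.25 to −0.13. The dilution argument survives, because it does not need ICCy above zero.
3. *The GEE uses both periods.* A reader might infer that the crossover's within-patient information goes unused, or that the GEE result has no clear meaning. The documents support neither. The GEE uses that information, and its planned term is the interaction, from which a factor acting equally on both drugs cancels. Only an index main effect would blend B with W. Even that rests on the plan's silence about splitting the index.
4. *A difference regression is no cure-all.* It assumes one slope common to both drugs. It is imprecise if the two drugs give similar indices. It leaves factors that differ between drugs within a patient, such as adherence, dose and weight. This stands, as limits on the added analysis.

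**Conclusion.** The point holds for the per-drug regressions and the paired tests. The regressions compare different patients, the paired tests cannot estimate an association, and no planned analysis isolates the within-patient link that section 1.3 puts forward.

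The size depends on assumptions that the documents do not supply. With stable patient differences in both the index and HRV change, per-drug rejection of a null within-patient association at n=38 is about 12% to 59%, against 5% within patients. With an HRV-change ICC of 0 there is no inflation, but a within-patient slope with no patient-level counterpart is reduced to roughly (1 − index ICC) of its value.

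It would go too far to conclude that confounding is present in this trial or that the per-drug regressions are the wrong analysis for the per-phase objective. The former would need a patient-level correlation that the documents do not report, and the latter contradicts the stated objective. The endpoint is exploratory, and no primary, secondary or safety result changes.

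**What to change.** In section 12.2:

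- Add a within-patient regression: each patient's difference in HRV change (dapagliflozin minus glimepiride) on the same patient's difference in the CGM index, with a sequence term to absorb the period effect. Report the slope with its 95% confidence interval, and state that it assumes a common slope across drugs.
- Keep the per-drug regressions for the per-phase objective, labelled as between-patient.
- If an index main effect is reported from the GEE, enter the index as patient mean plus deviation from that mean, and interpret the deviation term.
- Restrict the paired t-test or Wilcoxon step to comparing the indices between drugs.

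The cost is a few sentences and a few lines of code, with no new data. The price is precision: the within-patient slope will have a wide interval if most patients show similar indices on both drugs, and the report should say so.
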